3.3 Secondary Endpoints

Proportion of patients achieving complete or partial remission where the responses are defined as below:

- a) Complete Response at 12 months
 - < 300 mg proteinuria/24 hours
 - No greater than a 15% reduction in GFR as determined by creatinine clearance
- b) Partial Response at 12 months
 - > 50% reduction in 24 hour proteinuria
 - No greater than a 30% reduction in baseline GFR as determined by creatinine clearance
- c) No Response at 12 months
 - \leq 50% reduction, unchanged or increasing proteinuria over baseline levels

- A greater than a 30% reduction in baseline GFR as determined by creatinine clearance
- d) Improvement in hematuria (Categorical: <3 rbc/hpf; 3-10 rbc/hpf; 10 to 50; 50 to 100; >100 rbc/hpf)
- e) Improvement in complement 3 level (increase of 25% from baseline)

4 Subject Selection Enrollment and Withdrawal

4.1 Inclusion Criteria

- Age \geq 18 years of age
- Renal biopsy read at Mayo Clinic confirming the diagnosis of PGNMID or C3 GN
- In cases of C3GN serum electrophoresis with immunofixation should confirm presence of monoclonal gammopathy
- Proteinuria \geq 1000 mg over 24 hours
- eGFR \geq 20 mL/min/SA
- Subjects able and willing to give informed consent

4.2 Exclusion Criteria

- Pregnancy
- Seropositive for human immunodeficiency virus (HIV)
- Seropositive for hepatitis B (defined as a positive test for hepatitis B surface antigen [HBsAg] Subjects with resolved infection (ie, subjects who are HBsAg negative but positive for antibodies to hepatitis B core antigen [anti-HBc] and/or antibodies to hepatitis B surface antigen [anti-HBs]) must be screened using real-time polymerase chain reaction (PCR) measurement of hepatitis B virus (HBV) DNA levels. Those who are PCR positive will be excluded. EXCEPTION: Subjects with serologic findings suggestive of HBV vaccination (anti-HBs positivity as the only serologic marker) AND a known history of prior HBV vaccination, do not need to be tested for HBV DNA by PCR)
- Seropositive for hepatitis C (except in the setting of a sustained virologic response [SVR], defined as aviremia at least 12 weeks after completion of antiviral therapy).
- Multiple myeloma
- Anemia with Hgb $<$ 8.5 g/dL
- Thrombocytopenia with platelet count $<$ 100,000
- Leukopenia with WBC $<$ 3.5
- Any other disease, metabolic dysfunction, physical examination finding, or clinical laboratory finding giving reasonable suspicion of a disease or condition that contraindicates the use of an investigational drug or that may affect the interpretation of the results or render the patient at high risk from treatment complication
- Unable to provide consent
- Patients receiving therapy with oral prednisone or glucocorticoid equivalent in the last 6 weeks. Patients treated with low dose oral prednisone or glucocorticoid are allowed to be included if they are taking the medication for conditions unrelated to PGNMID or C3GN (e.g., asthma, gout) at a daily dose of 10mg or less.
- Patients who had received immunosuppressive therapy with cyclophosphamide, in the last 3 months

- Patients treated with MMF, cyclosporine, tacrolimus or azathioprine are allowed to be included if proteinuria has not improved or is worsening despite these medications and/or kidney function is worsening despite treatment with any of these medications. Once treatment with daratumumab is started, these medications will be discontinued.
- Patients who received rituximab previously with CD20 count of zero at the time of enrollment

4.3 Subject Recruitment, Enrollment and Screening

- Patients will be recruited from the principal investigator or co-investigator clinical practices
- Referring nephrologist within the Division of Nephrology and Hypertension at Mayo Rochester
- Review of renal biopsies and lab values conducted as part of clinical care
- Patients will receive \$1000 remuneration total for study participation (\$40 per completed study visit). Five hundred dollars will be given after completion of the 16th and final infusion, which is study visit Day 162. Five hundred dollar will be given after completion of the final visit on Day 365. If the patients withdraw from the study for any reason, they will receive prorated remuneration at \$40 per completed study visit.

4.4 Early Withdrawal of Subjects

4.4.1 When and How to Withdraw Subjects

- Subjects decision to withdraw from the study (withdrawal of consent)
- Failure of subject to adhere to protocol requirements (missing more than two infusions within the first 8 weeks or more than three infusions in the following 4 months). If a patient experiences an adverse event and the PI determines the next dose must be delayed, the dose may be delayed for up to 4 weeks and continue on the protocol schedule without being withdrawn.
- Disease progression (> 50% increase in proteinuria and > 30% reduction in GFR as measured by creatinine clearance) at day 77 visit
- Severe infection (defined as the development of pneumonia, severe urinary tract infection/pyelonephritis, sepsis, meningitis)
- If Hgb < 8.0 g/dL or platelet < 50,000, or WBC < 3.0 or absolute neutrophil count (ANC) < 500, the infusion will be held and restarted once blood counts have improved.

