3.1 General Design

This study is an open-label phase 2 trial of the safety and efficacy of daratumumab, in the treatment of PGNMID and C3GN associated with monoclonal gammopathy. Subjects will be screened at outpatient Nephrology Clinic visit appointments and interested qualified subjects will be consented and offered participation in this trial. Once consent has been obtained baseline values will be established and subjects will begin treatment and follow-up for the next 12 months. Daratumumab will be administered once weekly for 8 weeks and then once every 2 weeks for 8 additional doses. Patients will be followed for a total of 12 months (6 months after the last infusion). A final visit for evaluation and collection of lab samples will be conducted at the end of the study.

3.2 *The clinical course of the patients who have achieved complete or partial remission following daratumumab is unclear, therefore these patients who have consented to the OLE and achieved complete or partial remission, will be followed for 24 months following completion of the main trial. In the OLE, patients will be assessed every 3 to 6 months. Relapse is defined as a 30% increase in proteinuria from the lowest level the patient has achieved and will be documented with two 24 hour urine collections two weeks apart. If there is evidence of relapse, patients will receive 12 additional doses of daratumumab(16 mg/kg). The first 8 doses will be given weekly and the last 4 doses will be administered every other week. Primary Endpoints*

Incidence of major infection (defined as the development of pneumonia, severe urinary tract infection/pyelonephritis, sepsis, meningitis), grade 3 or 4 anemia, leukopenia or thrombocytopenia and changes in HgB, WBC count and platelet count from baseline to 6 month and 12 month timepoints.

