4.4.2 Data Collection and Follow-up for Withdrawn Subjects

- Subjects that withdraw consent or are withdrawn from the study due to safety issues or not following through with the protocol will be followed clinically by the PI or co-investigators or will be sent back to the referring nephrologist

5 Study Drug

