5.5 Subject Compliance Monitoring

This drug is administered intravenously in the CRU and we can ensure compliance. If patient misses more than one infusion within the first 8 weeks or more than two infusions in the following 4 months the subject will be withdrawn from the study. We will continue to follow the subject as part of the research study with blood and urine studies and clinic visits to ensure safety.

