7.2 Statistical Methods

Descriptive Statistics

Univariate descriptive statistics and frequency distributions will be calculated, as appropriate for all variables. Baseline values for demographic, clinical, and outcome variables (primary and secondary) in each response category will be tabulated. Time-to-response will be analyzed descriptively with Kaplan-Meier method.

For the primary endpoint, the number and proportion of patients with treatment-emergent major infections, grade 3 or 4 anemia, leukopenia or thrombocytopenia will be summarized. Changes in Hgb, WBC count and platelet count from baseline (Day 0) will be analyzed through a paired t-test by comparing post-baseline to baseline values. The secondary endpoint of the proportion of patients with complete or partial response will be summarized in a similar manner.

It is expected that 9 patients will enter the OLE. The rate of relapse in addition to the time to relapse from the last dose of daratumumab to initiation of retreatment will be evaluated. Paired t-test will be used to evaluate change in the proteinuria from time of relapse to the end of the study. Rate of CR and PR will be evaluated at the end of the OLE.

Handling of Missing Data

This is a study of only 12 patients and expect that majority of patients will have complete data available.

Primary Hypothesis: Daratumumab is safe and well-tolerated in patients with PGNMID and C3GN associated with monoclonal gammopathy

To test this hypothesis, the incidence of major infection will be examined, specifically the development of pneumonia, severe urinary tract infection/pyelonephritis, sepsis, meningitis will be reported. In addition, anemia, leukopenia, thrombocytopenia will be examined by evaluating changes in Hgb, WBC count and platelet count, respectively. Statistical significance will be assessed using paired t-test comparing 6 months and 1 year value compared to baseline. The

number of patients who had to discontinue drug due to side effect (drop in blood counts, infection) will also be reported.

Secondary Hypothesis: Daratumumab is effective in inducing remission (defined as improvement in proteinuria and eGFR) in patients with PGNMID and C3GN associated with monoclonal gammopathy

A paired t-test will be performed to assess change in proteinuria and renal function at 6 months and 12 months compared to baseline (screening visit).

Interim Analysis

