7.2 Subject Population(s) for Analysis

All-treated population: Any subject that received at least one dose of study drug.

8 Safety and Adverse Events

The primary side effects associated with daratumumab include anemia, neutropenia and thrombocytopenia and these will be evaluated initially by monthly CBC done on Day 21, 49, 77, 105, 133, 161 and then every 3 months done on Day 264, 365. Further, these will be evaluated during OLE laboratory assessments.

Other side effects include risk of infection specifically pneumonia and patients will be asked about any signs of symptoms suggestive of infection (e.g fever, cough) or any hospitalization, emergency department visits or other doctor visits at the clinical visits on Day 49, 77, 133, 161, 264, 365 and during OLE when laboratory assessments are completed or an infusion is administered. Other side effects include symptoms of nausea and fatigue and similarly patients will be asked regarding these symptoms at the time of clinic visits and during OLE when laboratory assessments are completed or an infusion is administered.

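### Withdrawal for severe infection uses the primary infection definition, and no study blood counts are planned afterwards, so the primary paired t-tests can lose the infected patients

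*Combined protocol and SAP*

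**What the plan says.** - **Withdrawal.** Section 4.4.1 gives as one reason "Severe infection (defined as the development of pneumonia, severe urinary tract infection/pyelonephritis, sepsis, meningitis". No time window is attached, whereas the disease-progression reason in the same list is tied to the Day 77 visit.
- **Primary endpoint, infection part.** The Primary Endpoints text of Section 3.2 reads "Incidence of major infection (defined as the development of pneumonia, severe urinary tract infection/pyelonephritis, sepsis, meningitis". The four infections are the same.
- **Primary endpoint, blood-count part.** The same text adds "changes in HgB, WBC count and platelet count from baseline to 6 month and 12 month timepoints". Section 7.2 says "Statistical significance will be assessed using paired t-test comparing 6 months and 1 year value compared to baseline".
- **After withdrawal.** Under Section 4.4.2, patients who withdraw consent, are withdrawn for safety, or do not follow the protocol "will be followed clinically by the PI or co-investigators or will be sent back to the referring nephrologist". No study blood counts are specified. Section 5.5 says, of patients withdrawn for missed infusions, "We will continue to follow the subject as part of the research study with blood and urine studies and clinic visits to ensure safety".
- **Blood-count days.** The opening of Section 8 schedules "monthly CBC done on Day 21, 49, 77, 105, 133, 161 and then every 3 months done on Day 264, 365". The 6-month count is therefore Day 161 and the 12-month count Day 365.
- **Population and missing data.** The analysis population is everyone who received at least one dose. Section 7.2 gives no method for missing values; it only expects that most patients will have complete data.

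**The concern.** One part of the primary endpoint triggers removal from the study, and the other part needs values measured after that removal. A paired t-test uses only patients who have both values. If the plan is followed as written, the blood-count tests cover only patients without an earlier major infection (subject to the other withdrawal reasons), while the stated population is all treated.

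The loss is tied to a safety outcome, so it cannot be assumed to be random. If patients with a major infection also have different blood-count changes, the estimated mean change is off for the treated group. With 12 patients, one or two such losses are a visible fraction of the data.

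**Working it through.** There is no sample-size figure to reproduce: Section 7.1 sets 12 patients without a power calculation and states no effect, SD or dropout rate.

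**1. Which counts are at risk.** Eight weekly infusions fall on Days 1, 8, ..., 50. Eight two-weekly infusions follow on Days 50 + 14j for j = 1 to 8, so the last is Day 50 + 112 = Day 162, which agrees with Section 4.3. The 6-month count on Day 161 is taken the day before.

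| Major infection occurs | Day 161 count | Day 365 count |
|---|---|---|
| Before Day 161 | not planned | not planned |
| After Day 161 | already taken | not planned |

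**2. How many patients.** Inputs: n = 12 (Section 7.1) and p = 0.11. The latter is the pneumonia figure in Section 1.4, the only infection rate given that matches the definition. It comes from earlier daratumumab use and covers one of four qualifying infections. Applying it to this trial's follow-up is an assumption.

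- Expected number = 12 × 0.11 = 1.32.
- P(at least 1) = 1 − 0.89^12 = 1 − 0.247 = 0.753.
- P(at least 2) = 1 − 0.247 − 12 × 0.11 × 0.89^11 = 1 − 0.247 − 0.366 = 0.387.

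Over an assumed range of rates:

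| Rate | Expected of 12 | P(at least 1) | P(at least 2) |
|---|---|---|---|
| 5% | 0.6 | 46.0% | 11.8% |
| 11% | 1.3 | 75.3% | 38.7% |
| 20% | 2.4 | 93.1% | 72.5% |
| 30% | 3.6 | 98.6% | 91.5% |

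These figures count infections at any time, so they apply to the Day 365 test. For the Day 161 test only infections before that day matter, and the numbers are at most these.

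**3. Shift in the mean change.** Let k patients be missing, let m be the mean change in the 12 − k observed patients, and let the missing patients' mean differ from m by a gap g, in SD units. The all-treated mean is [(12 − k)m + k(m − g)]/12 = m − kg/12, so the observed mean is off by kg/12.

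| k | g = 0.5 SD | g = 1 SD | g = 2 SD |
|---|---|---|---|
| 1 | 0.04 | 0.08 | 0.17 |
| 2 | 0.08 | 0.17 | 0.33 |

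The documents give no value for g, nor its sign.

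**4. Precision.** For a paired t-test at two-sided 0.05 (assumed, since no level is stated), noncentral-t power for a change of 0.89 SD is 80.1% with 12 pairs, 75.8% with 11 and 70.8% with 10. The change detectable with 80% power goes from 0.89 SD to 0.94 SD and 1.00 SD.

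**The case against.** Several stronger readings are tempting, and the documents do not support them.

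- **That the counts cannot be obtained at 6 and 12 months in any infected patient.** An infection after the last dose on Day 162 comes after the Day 161 count, so only Day 365 is at risk. Section 4.4.2 does not forbid collecting counts, and clinical follow-up by the investigators may yield some. Section 5.5 shows that research bloods after withdrawal are foreseen for at least one reason. What stands is that no such counts are planned after an infection withdrawal.
- **That the test covers only patients who tolerated the drug.** For low blood counts, Section 4.4.1 says "the infusion will be held and restarted once blood counts have improved". It also allows a dose to be delayed by up to 4 weeks for an adverse event without withdrawal. Patients with the toxicity that this test measures therefore generally stay in. A longer delay might lead to withdrawal, but that is inference.
- **That the rule certainly applies after the last dose.** This is inferred from the absence of a time limit; the section does not address it.
- **That the safety conclusion as a whole is compromised.** The number and proportion with major infection and grade 3 or 4 cytopenia are summarized separately. The infection and any such cytopenia before withdrawal are counted there. Section 7.2 also reports discontinuations for infection or a drop in counts. The problem is confined to the change-from-baseline tests.
- **That the bias has a known direction and size.** Infection and low white counts might plausibly go together, but the documents quantify no link between infection and any blood count. An illustration in g/dL of hemoglobin would be invented.

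The identical definitions, the conflict between Sections 4.4.2 and 5.5, and the absent missing-data method survive all of this.

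**Conclusion.** The concern holds in limited form and should be fixed. Following the plan as written loses outcome-related blood-count data: both tested time points for infections before Day 161, and Day 365 only for later ones. The paired t-tests then do not describe the all-treated population.

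About one patient in 12 is expected to be affected at the 11% figure, with a 75% chance of at least one and 39% of at least two. This assumes that an earlier pneumonia rate carries over and ignores the other three infections. The shift of 0.04 to 0.33 SD rests wholly on the assumed gap and on one or two missing patients.

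**What to change.** - **Reconcile Sections 4.4.1, 4.4.2 and 5.5** so that stopping study drug is distinct from leaving the study, and say which follow-up applies to each reason for withdrawal. The treatment rule itself stays as it is.
- **Keep the counts.** Unless consent is withdrawn, patients who meet the severe-infection criterion have the already scheduled blood counts through Day 365, including when the infection follows the last infusion. State in Section 7.2 that these values enter the all-treated analysis and how any values still missing are handled.
- **Optional supportive analysis.** Fit a repeated-measures model to all scheduled counts (screening and Days 21, 49, 77, 105, 133, 161, 264 and 365), with a simple covariance structure and a small-sample degrees-of-freedom correction. It uses counts taken before withdrawal but assumes that missingness depends only on observed data. It would not in general remove bias from dropout that depends on the unobserved change, so it does not replace collecting the counts.

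The cost is protocol wording plus a few visits already in the schedule, for about one or two patients. The downside is that some retained values reflect time off drug; reporting whether each count was taken on or off treatment would make that visible.

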4.4.2 Data Collection and Follow-up for Withdrawn Subjects

- Subjects that withdraw consent or are withdrawn from the study due to safety issues or not following through with the protocol will be followed clinically by the PI or co-investigators or will be sent back to the referring nephrologist

5 Study Drug

5.1 Description

Daratumumab is an IgG1-kappa human monoclonal antibody that binds to the CD38 transmembrane glycoprotein on the surface of tumor cells and induces apoptosis. It appears in liquid form and is administered intravenously.

5.2 Treatment Regimen

The drug will be given intravenously at a dose of 16 mg/kg once weekly for 8 weeks followed by once every 2 weeks for 8 additional doses

If there is evidence of relapse, patients in OLE will be treated with 12 doses of daratumumab (16 mg/kg). The first 8 doses will be given weekly and the last 4 doses will be administered every other week.

5.3 Method for Assigning Subjects to Treatment Groups

This study is non-randomized trial and all 12 patients that are enrolled in this study will receive daratumumab.

5.4 Preparation and Administration of Study Drug

Study drug will be prepared in the research pharmacy.

Pretreatment: Fifteen minutes prior to the first infusion, 100 mg methylprednisolone will be administered via IV along with 1000 mg acetaminophen and 50 mg diphenhydramine given by mouth. Fifteen minutes prior to all subsequent infusions, only 1000 mg acetaminophen and 50 mg diphenhydramine will be administered by mouth.

First Infusion and those part of OLE being retreated due to relapse (16 mg/Kg): IV infusion in 1000 mL 0.9% NaCl via 0.2 or 0.22 micron in-line filter, beginning at 50 mL/hr. Increase by 50 mL/hr every 60 minutes, as tolerated, to a maximum rate of 200 mL/hr. Vital signs will be taken every 15 minutes for first hour, then every hour until end of infusion, and then again after IV flush.

Second Infusion (16mg/Kg): IV infusion in 500 mL 0.9% NaCl via 0.2 or 0.22 micron in-line filter, beginning at 50 mL/hr. Increase by 50 mL/hr every 60 minutes, as tolerated, to maximum rate of 200 mL/hr. If the first infusion was not well tolerated (infusion-related reaction > Grade 1), then instructions for the first infusion should be used. Vital signs will be taken every 15 minutes for first hour, then every hour until end of infusion, and then again after IV flush.

Subsequent Infusions(16 mg/Kg): IV infusion in 500 mL 0.9% NaCl via 0.2 or 0.22 micron in-line filter, beginning at 100 mL/hr. Increase by 50 mL/hr every 60 minutes, as tolerated, to maximum rate of 200 mL/hr. If the previous infusion was not well tolerated (infusion-related reaction > Grade 1), then instructions for the second infusion will be used. Vital signs will be taken every 15 minutes for first hour, then every hour until end of infusion, and then again after IV flush.

Infusion related reactions: Diphenhydramine 25 mg IV can be given every 4 hours as needed and may repeat once if symptoms are not relieved within 15 minutes of initial dose. Methylprednisolone 100 mg IV can be given as needed for infusion related reactions.

Post-infusion: All patients should receive dexamethasone 4 mg by mouth once daily with food for two days beginning the day after daratumumab. In addition, acyclovir 400 mg by mouth twice daily, beginning within one week of starting daratumumab, and continuing for 3 months after the last daratumumab infusion. Beginning the day after their first daratumumab infusion, patients will also start single strength Bactrim once a day (or its equivalent) to prevent opportunistic infections, including pneumocystis pneumonia. Treatment with Bactrim will continue for six months after the last daratumumab infusion.

A worksheet will be created specifically for this study, which would include a dose calculation with a double check by another pharmacist for added safety. The drug will be prepared in the following steps.

1. Prepared in the non-hazardous sterile hood.
2. Drug volume calculated based upon the 16 mg/kg dose.
3. Utilize 0.9% 1000 mL for the first dose, then 0.9% 500 mL for subsequent doses.
4. Remove drug volume from 0.9% IV bag.
5. Infusion rate instructions:

Continuous Infusion: 1st and 2nd doses: Start infusion at 50 mL/hr. Rate may be increased by 50 mL/hour every hour to a maximum rate of 200 mL/hour.

Subsequent doses: Start infusion at 100 mL/hr. Rate may be increased by 50 mL/hour every hour to a maximum rate of 200 mL/hour.

6. Light protect IV bag.

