1.4 Dose Rationale and Risk/Benefits

The dose of daratumumab that has proven to be effective in patients with multiple myeloma is 16 mg/kg started once weekly for 8 weeks followed by every other week for 16 weeks, and then once every 4 weeks thereafter. We will be using similar dose (16 mg/kg) and similar dosing interval for a total of 16 doses over a 24 week period. The drug is only available to be administered intravenously and we aim to use the same route of administration.

Daratumumab overall is well-tolerated. The most common side-effect is infusion-related reaction (48%). We aim to use the same pre and post treatment regimen (including corticosteroid, diphenhydramine and acetaminophen) as has been done in the previous trials. Serious adverse effects include anemia, grade 3 or 4 (19%), lymphocytopenia grade 3 or 4 (40%), neutropenia, grade 3 or 4 (20%), thrombocytopenia, Grade 3 or 4 (18%), and increased risk of infection specifically pneumonia (11%). Common adverse effects include nausea (27%), anemia all grades (45%), lymphocytopenia all grades (72%), neutropenia all grades (60%), thrombocytopenia all grades (48%), backache (23%), cough (21%), upper respiratory infection (20%), fatigue (39%), fever (21%).

The treatment options for patients with PGNMID or C3GN associated with monoclonal gammopathy are limited with variable success. If untreated, majority of patients will progress to endstage renal disease. The current therapeutic options include rituximab vs. cyclophosphamide and prednisone with or without bortezomib. Daratumumab has a similar if not better side-effect profile to the above-mentioned treatment options and therefore we believe the risks associated with daratumumab are acceptable.

2 Study Objectives

Primary Objective

To assess the safety of daratumumab in patients with PGNMID or C3GN associated with monoclonal gammopathy.

Secondary Objective

To assess the efficacy of daratumumab in inducing complete or partial remission in patients with PGNMID or C3GN associated with monoclonal gammopathy as measured by change in proteinuria and serum creatinine.

3 Study Design

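### The 6-month paired test of renal function compares a creatinine-based value taken on mandated Bactrim (or its equivalent) with a screening value taken before it, so it should not be read alone as a change in GFR

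*Combined protocol and SAP*

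**What the plan says.** Section 5.4 (Post-infusion): beginning the day after the first infusion, "patients will also start single strength Bactrim once a day (or its equivalent" as infection prophylaxis, and "Treatment with Bactrim will continue for six months after the last daratumumab infusion". Section 4.3 dates the last dose: "completion of the 16th and final infusion, which is study visit Day 162".

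Section 7.2 (Secondary Hypothesis): "A paired t-test will be performed to assess change in proteinuria and renal function at 6 months and 12 months compared to baseline (screening visit". The test does not define renal function, but every measure the plan names uses creatinine:

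- Section 2, secondary objective: "as measured by change in proteinuria and serum creatinine".
- Section 3.3, complete response: "No greater than a 15% reduction in GFR as determined by creatinine clearance". Partial response uses the same measure with a 30% limit.
- Section 7.2, definition of remission: "defined as improvement in proteinuria and eGFR".

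The Section 6 schedule lists no measure of kidney function that does not depend on creatinine. Section 5.3 makes the trial single-arm with 12 patients. Section 3.3 sets the response categories at 12 months. Section 3.1 describes follow-up this way: "Patients will be followed for a total of 12 months (6 months after the last infusion".

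**The concern.** The 6-month comparison changes two things at once: the patient has had a course of daratumumab, and has also begun a prophylactic drug that was absent at baseline. Trimethoprim, a component of Bactrim, reduces tubular secretion of creatinine. Serum creatinine can then rise, and creatinine clearance and eGFR fall, without a change in GFR. This is general pharmacology; the documents do not mention it.

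Every patient is assigned the prophylaxis on the same timetable, so nothing within the trial separates its effect from that of daratumumab. At stake is the reading of one of the two time points named for the renal part of the secondary hypothesis: a stable patient could appear to lose function, or a real gain could be missed. No primary endpoint or stopping rule depends on the test.

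**Working it through.** **Timing**

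1. Eight weekly doses fall on Days 1, 8, …, 50. Eight further doses every 14 days fall on Days 64, 78, …, 162. That gives 16 doses ending on Day 162, as Section 4.3 states.
2. Prophylaxis starts on Day 2. Six calendar months are 181 to 184 days, so on schedule it ends at 162 + 181 = Day 343 to 162 + 184 = Day 346.
3. The visits on either side of six months are Day 161/162 and Day 264. Both are on prophylaxis; by Day 161 a patient has had 161 − 2 + 1 = 160 days of it. Screening precedes it.
4. The margin at the final visit is 365 − 346 = 19 to 365 − 343 = 22 days. A last infusion about 19 to 22 days late, with the final visit kept at Day 365, removes the margin. Section 4.4.1 allows a dose to be delayed by up to 4 weeks and holds infusions for low counts, with no stated limit on repeats. A net delay of 28 days moves the end of prophylaxis to Day 371 to 374.

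**Size (illustrative)**

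The documents give neither an effect of prophylaxis on creatinine nor an SD of change. Assumptions: an apparent fall in clearance of a = 5%, with 10% as a higher case; SD of log change 0.15 to 0.30; paired t-test on the log scale; n = 12; two-sided 5%; no true change. Section 7.2 does not specify the log scale.

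With all 12 exposed, the noncentrality is ln(1 − a)/SD × √12. For a = 5% and SD 0.15 this is −0.0513/0.15 × 3.464 = −1.185. With 11 degrees of freedom and critical value 2.201, the chance of a significant result is 19.1%. Where only 6 or 9 patients take a trimethoprim-containing agent, the figures come from simulation (400,000 trials per cell).

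| Artefact | Exposed | SD 0.15 | SD 0.20 | SD 0.25 | SD 0.30 |
|---|---|---|---|---|---|
| 5% | 12 | 19% | 13% | 10% | 8% |
| 5% | 9 | 12% | 9% | 8% | 7% |
| 5% | 6 | 8% | 7% | 6% | 6% |
| 10% | 12 | 60% | 39% | 27% | 20% |
| 10% | 9 | 35% | 22% | 16% | 13% |
| 10% | 6 | 17% | 12% | 9% | 8% |

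**Direction**

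With a 5% artefact in all 12, almost all the significant results are apparent declines. The chance of a significant false improvement falls from the nominal 2.5% to 0.1 to 0.6%.

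**Hidden gain**

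With a true 10% rise and a 5% artefact in all 12, the mean log change is ln(1.10 × 0.95) = 0.044 instead of ln(1.10) = 0.095. The chance of detecting the rise falls from 52% to 15% at SD 0.15, and from 17% to 7% at SD 0.30.

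**The case against.** The strongest reply is that the mechanism and every effect size come from outside the documents. One single-strength tablet daily may do little, and an equivalent agent may contain no trimethoprim. This stands as a limit on size: a 3% artefact in all 12 gives only about 6 to 10%, and a 5% artefact with SD 0.40 to 0.50 only 6 to 7%. It does not remove the mismatch between baseline and 6 months, which rests on the protocol's own dates.

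Second, the bias is conservative. The hypothesis is improvement, and the artefact works against it. This is correct, and a reader who inferred that prophylaxis could produce a false efficacy finding would be wrong. An apparent loss or a missed gain still misinforms a proof-of-concept trial.

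Third, Section 3.3 already fixes response at 12 months, and the 6-month renal test is not listed there as an endpoint. This also stands: the plan does not give the two time points equal weight for response. Section 7.2 nevertheless names both for the paired test and says nothing about how the 6-month one should be read.

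Fourth, other things move creatinine. Section 4.2 stops cyclosporine, tacrolimus and similar drugs when daratumumab starts (although Section 5.6 expects patients to be off them already), and Section 5.6 allows ACE-inhibitor or ARB down-titration. Labelling the 6-month value will not make it clean.

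Fifth, the case report form is not among the documents and may already capture concomitant drugs. If so, the recording part of the fix costs less still.

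**Conclusion.** The point holds as a matter of interpretation and is cheap to address. Any 6-month renal value is on prophylaxis, its baseline is not, all named measures depend on creatinine, and there is no control arm. With the more plausible assumed artefact of 5%, the chance of a significant 6-month result without true change is about 8 to 19% if all 12 patients are exposed and 6 to 12% if 6 to 9 are. These figures depend on the assumed artefact, SD and log scale, and on the agent containing trimethoprim.

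Three stronger readings are not supported:

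- **That 60% false signals are to be expected.** That cell needs the larger artefact, full exposure and the smallest SD together.
- **That complete and partial response are compromised.** On schedule they are read 19 to 22 days after prophylaxis ends. However, Section 3.1 loosely equates 12 months with six months after the last infusion, which is also when prophylaxis stops. With permitted delays, Day 365 may be on prophylaxis for some patients; how many cannot be stated.
- **That the Day 77 withdrawal rule can be triggered by the artefact alone.** That rule also requires a rise of more than 50% in proteinuria.

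**What to change.** 1. Add to Section 7.2: 'The 6-month renal-function value is reported as an on-prophylaxis value and is not read alone as a change in GFR; the 12-month value, when off prophylaxis, is the main renal-function comparison with screening.'
2. At each creatinine-clearance collection, record the prophylactic agent and the date of its last dose. Flag any 12-month collection taken on a trimethoprim-containing agent. This settles patient by patient what the loose timing in Section 3.1 leaves open.
3. Report the 12-month paired test and complete/partial response as defined, plus a repeat that excludes flagged patients or lists them individually. Do not reclassify flagged patients on proteinuria alone: dropping the GFR criterion can only move patients towards response, and could count someone with a real fall of more than 30% as a responder.

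Prescribing, visit timing, response definitions and the Day 77 rule stay as they are. The cost is one sentence, two recorded items and one repeat analysis. The downside is less weight on the end-of-treatment renal value. The 12-month value comes about six months after the last infusion, so it reflects durability more than immediate effect, and withdrawals or exclusions may leave fewer pairs.
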